## 12.4 Statistical Analysis Plan

A detailed SAP in which all aspects of data analysis will be defined in detail and prepared prior to the blind break.

The SAP will include details of the following:

- Definitions of analysis populations
- Description of any data transformations and data derivations to be used together with rationale and references
- Details of the statistical methods to be conducted, together with methods used to estimate corresponding confidence intervals
- Details of methods for checking the appropriateness of the chosen statistical model
- Discussion of the use of covariates and subgroups
- Discussion of any multiplicity and adjustment procedures to be implemented.
- Methods of dealing with missing values and outliers together with details of any sensitivity analyses to be performed
- Specification of any subgroup or interaction analyses
- Example table and listing shells to indicate the proposed presentation of the data.

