7.2 Primary efficacy analyses

The hepatic fat fraction will be summarised and tabulated for the Baseline and Week 24 visits along with change from Baseline by randomised treatment group. Change in hepatic fat fraction from Baseline will be analysed using analysis of variance on the ITT, PP and FAS populations, where the model will include the treatment group and another subgrouping variable. As determined by baseline values, hepatic fat fraction categories ($\leq 10\%$, $>10\% - <21\%$, $\geq 21\% - <30\%$ and $\geq 30\%$), HbA1c group ($< 6\%$ and $\geq 6\%$), and ALT (greater or less than 1.5 x the upper normal limit) will be used to subgroup the analysis populations. Further, data from liver biopsies up to 6 months prior to screening will also be used to subgroup analysis populations based on fibrosis (0-1 vs. 2-3), NAS inflammation (0-1 vs. 2-3), and NAS ballooning (0-1 vs. 2). These will be used in addition to the main effects factors and the two-way interaction of those main effects.

In the primary analysis, any missing data will remain missing. Treatment effects between placebo and each of the active treatment groups within each of the hepatic fat and HbA1c categories will be generated and tested for significant differences between treatment and placebo using pre-specified contrasts.

To examine the effect of treatment within the various levels of these subgroup variables, a mixed models ANOVA will be employed if there are an appropriate number of observations in each cell (created by the crossing of study treatment and subgroup categories) and the data does not differ significantly from a normal distribution. In the event that this is not the case, the data will be ranked in an attempt to normalise it, and pairwise contrasts between treatment groups will be performed using Wilcoxon rank sum tests within each combination of visit and subgroup variable level will be performed. However, if the ranked data is also not normally distributed, a permutation test will be employed whereby the unranked data will be randomly sampled (Lehmann, 2006). No adjustment for multiple testing will be made. See Appendix 1 for more information on both the Wilcoxon rank-sum test and the permutation test.

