13. APPENDIX 1 – EXTENSION OF WILCOXON RANK-SUM TEST FOR CLUSTERED DATA

Adapted from Lehmann, 2006:

To compare each one of the treatment arms to the placebo arm separately, perform the following steps:

1. Each FF category at baseline will be defined as a separate cluster.
2. Within each cluster, rank all values (treatment and placebo together)
3. Calculate w_i which is the sum of ranks of the treatment group in each cluster separately.

$$W = \sum_{i=1}^M w_i$$

4. Calculate W while M is the total number of clusters.
5. The best way to test W is by using a **permutation test**. This may be computationally too complex to apply. If so, there is a normal distribution approximation we can use but it is less accurate, especially in our small sample so, if possible, we advise to try and use the permutation test.

The permutation should be performed so we protect the data of each cluster separately and also protect the cluster design of the sample.

More specifically, Let us define:

n_i - the number of observations in cluster i .

n_{i0} - the number of observations in cluster i , in the placebo arm.

n_{i1} - the number of observations in cluster i , in the treatment arm.

Each permutation will be calculated by randomly sampling n_{i1} values within each cluster from the n_i values available and calculating the rank sum of those values. Going over all possible permutation of the data under this design.

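### SAP 7.2 uses a normality check on ranks to choose between Wilcoxon and a permutation test within subgroup levels; on pooled ranks that check sees only the level size and the normality test used

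*SAP*

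**What the plan says.** SAP 7.2 lists six subgroup variables: hepatic fat fraction (four categories), and HbA1c, ALT, fibrosis, inflammation and ballooning (two levels each). That is 4 + 5 × 2 = 14 levels, or 28 dose-placebo comparisons in each analysis population.

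One paragraph says, without condition, that effects within the fat-fraction and HbA1c categories "will be generated and tested for significant differences between treatment and placebo using pre-specified contrasts". The next opens "To examine the effect of treatment within the various levels of these subgroup variables" and sets out a ladder:

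- A mixed-model ANOVA is used "if there are an appropriate number of observations in each cell" and the data do not depart significantly from normality.
- Failing that, "the data will be ranked in an attempt to normalise it", with pairwise Wilcoxon rank-sum tests within each visit and subgroup level.
- Finally, "if the ranked data is also not normally distributed, a permutation test will be employed whereby the unranked data will be randomly sampled".

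Section 7.2 refers to Appendix 1 for both fallback tests. Appendix 1 takes each baseline fat-fraction category as a cluster. Its ranking step is "Within each cluster, rank all values (treatment and placebo together", and the treatment rank sums are then added over clusters. Its permutation draws, within each cluster, from the "values available and calculating the rank sum of those values".

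The SAP names no normality test, significance level or unit of checking (pooled, by arm or residuals). Protocol 12.4 lists among the SAP's contents "Details of methods for checking the appropriateness of the chosen statistical model". The sample table shells in SAP section 12 have group-comparison columns for change, ranks, permutations and disparity, and do not say which result counts.

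**The concern.** A normality check is meant to learn something about the data, but ranking two arms together removes the shape of the data before the check is made. The answer is then known from the number of patients alone. Nor is the check needed: the Wilcoxon null distribution comes from how ranks fall between the arms, not from normal ranks, and a permutation test does not need normality either.

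What is at stake is which method applies in the larger subgroup levels. Level size and an unstated choice of normality test would decide it, and two levels of the same variable could be analysed differently because of their sizes. This matters most when changes are skewed or heavy-tailed, which is the case the ladder was written for. SAP 7.3 carries the same inferential basis over to secondary and exploratory endpoints, so the ambiguity may spread.

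**Working it through.** **1. The protocol's own figure.** Protocol 12.1 assumes an SD of 6 at each time point and a correlation of 0.25. SD of change = √(36 + 36 − 2 × 0.25 × 36) = √54 = 7.35 (stated as 7.3). With 40 per arm, a difference of 5, SD 7.3 and two-sided α = 0.05, power is 0.857 (noncentral t) or 0.865 (normal approximation). The stated 85% is reproduced, and it does not pass through the ladder.

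**2. What the rank check sees.** Untied pooled ranks of n patients are 1, 2, …, n, whatever the values. Normal, lognormal, Cauchy and exponential samples of equal size gave the same Shapiro-Wilk p (0.3335 at n = 27; 0.1241 at 40; 0.0066 at 80). The p-values on 1..n are:

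| n | Shapiro-Wilk | Anderson-Darling | Lilliefors |
|---|---|---|---|
| 20 | 0.551 | 0.806 | 0.99 |
| 40 | 0.124 | 0.299 | 0.925 |
| 60 | 0.028 | 0.089 | 0.819 |
| 80 | 0.0066 | 0.026 | 0.687 |
| 120 | 0.0005 | 0.0021 | 0.406 |

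The first n with p < 0.05 is 29 for D'Agostino-Pearson, 52 for Shapiro-Wilk, 70 for Anderson-Darling and 100 for Jarque-Bera. For Lilliefors it is 232 or 251, depending on the p-value approximation, and so beyond the 120 patients planned. As shares of the 80 patients in two arms: 29/80 = 36%, 52/80 = 65%, 70/80 = 88%; the other two cannot be reached in a two-arm comparison. Ties hardly matter: rounding values to 0.1 never changed the Shapiro-Wilk decision at the sizes tried (n = 27 to 120), and rounding to whole percent changed it in at most 0.3% of runs.

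**3. An illustrative split.** The documents give no level sizes, so a 70/30 split is assumed. The larger level has 0.7 × 40 = 28 per arm (n = 56, Shapiro-Wilk p = 0.037) and goes to a permutation test. The smaller has 0.3 × 40 = 12 per arm (n = 24, p = 0.42) and keeps Wilcoxon. Under Anderson-Darling or Lilliefors both keep Wilcoxon.

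**4. Consequence for the verdict.** The ladder was simulated with 28 per arm, SD 7.35 and a 5-point effect. A normality test on pooled within-arm residuals at 0.05 led to a t-test if passed. If failed, the same test was applied to the pooled ranks, leading to Wilcoxon if passed and a permutation test if failed. Shapes are assumed. Shapiro-Wilk against Anderson-Darling:

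| Changes | Verdicts differ, raw means permuted | Power, raw means permuted | Verdicts differ, rank sums permuted |
|---|---|---|---|
| Normal | 0.2% | 73% v 73% | not run |
| t, 3 df | 11.5% | 79% v 90% | 1.1% |
| Exponential | 20.2% | 72% v 91% | 0.7% |

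The raw-mean columns use 2000 trials and the rank-sum column 1500. Repeat raw-mean runs gave 11.7% and 13.7% (t) and 20.1% and 19.5% (exponential). A further run gave about 13-18% for raw means and about 1.6% for rank sums. With rank sums, power is about 90% v 90% (t) and 91% v 91% (exponential). In the raw-mean version, Shapiro-Wilk verdicts at 12 per arm differ from those of the other two tests in at most 2.5% of trials, and type I error is 4.4-5.9% throughout. Monte Carlo error is about 1 percentage point.

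**5. If ranks are checked by arm.** Shapiro-Wilk was applied to each arm's share of the pooled ranks, rejecting if either arm gave p < 0.05. At 20 per arm this happens in about 6% of trials with no effect. With a 5-point effect it happens in 9% (normal), 19% (t) or 61% (exponential). At 10 per arm the figures are 0.3-0.5% with no effect and 0.4%, 1.4% or 4.4% with one.

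**The case against.** The strongest reply is that Appendix 1 defines the permutation test and uses rank sums. Sampling unranked values in 7.2 could mean drawing values and then summing their ranks. The last step would then mainly replace an asymptotic Wilcoxon p-value with a permutation one, with almost no consequence. This stands as a limit on size. It does not rescue the rule, and it does not settle the reading: 7.2 sets unranked against ranked data and names no statistic, and it works within one level while Appendix 1 adds over fat-fraction categories.

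Several stronger inferences are tempting but not supported:

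- *That the check never responds to the data.* This is exact only for pooled, untied ranks. 7.2 does not fix the unit of checking, and by arm the check responds to the treatment effect and, through it, to shape. That is no better as a basis for choosing a test.
- *That every level holding 65% of patients is affected.* That threshold belongs to Shapiro-Wilk on two arms at full size. At the interim, two arms hold about 80 × 2/3 = 53 completers, so a level would need nearly all of them.
- *That only one result will be reported.* The table shells appear to show all of them; the gap is which one counts.
- *That the primary result or type I error is compromised.* The ladder is written for subgroup levels, and the simulated error rate stays near 5%.
- *That the normality check on the raw changes is equally invalid.* It does look at the data; it is underspecified.

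The trial is also declared exploratory, without multiplicity adjustment (protocol section 12). That lowers the importance but gives the rank check no purpose.

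**Conclusion.** The point holds and is modest in size. Choosing between Wilcoxon and a permutation test by the normality of ranks is invalid: with pooled ranks it reflects level size and an unnamed normality test. The conflict between 7.2 and Appendix 1 on the permutation statistic decides how much this matters. For a larger level with clearly non-normal changes, verdicts differ between Shapiro-Wilk and Anderson-Darling in roughly 12-20% of trials if raw means are permuted, and in about 1-2% if rank sums are. With normal changes or in small levels almost nothing changes. These sizes rest on assumed shapes, an assumed 70/30 split and the protocol's SD and 5-point effect; the algebra of the ranks rests on none of these.

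**What to change.** - Delete the rank-normality step from SAP 7.2.
- Take subgroup-level effects from contrasts in the linear model of the protocol synopsis (baseline hepatic fat fraction as covariate, stratification factors, treatment), adding the treatment-by-subgroup term.
- Pre-specify one rank-based check, reported whatever any normality result: the Wilcoxon rank-sum statistic with a permutation p-value. Use the Appendix 1 stratified form for the overall comparison and the two-arm form within a level.
- Make 7.2 and Appendix 1 name the same statistic.
- State in the table shells that the model contrast is the result that counts. A normality check on raw changes can then stay as a named diagnostic.

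The cost is SAP rewording and somewhat simpler programming. There is a statistical price: at 28 per arm with non-normal changes, an unadjusted model contrast has less power than Wilcoxon (75% v 90% for t with 3 df; 71% v 90% for exponential). That is why the fixed rank check is kept. With normal changes the order reverses slightly (about 71% v 68%). The baseline covariate offsets part of the loss: with the protocol's inputs the residual SD is 6 × √(1 − 0.25²) = 5.81 instead of 7.35, which for normal data raises power at 28 per arm from 71% to about 89%.

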
Sample size determination:
	
Fat Liver Content Change from Baseline:                  The current sample size of 40 subjects per group should yield approximately 85% power to detect a treatment effect of at least -5% with respect to the difference in the mean change from Baseline between one of the IMM-124E treatment groups and placebo assuming a standard deviation (SD) of 7.3% (<math>\alpha=0.05</math>; two-tailed; unpaired t-test). The SD of 7.3% for the change from Baseline endpoint was derived assuming 1) SDs of 6% for each timepoint, 2) equal variances in each treatment group and 3) a low to moderate correlation of 0.25 between pre- and post-Baseline measurements.
 
Sample size and power estimates have not been adjusted for multiple comparisons or multiple endpoints, dropouts or stratification.
 
The analysis of each primary endpoint will be based on a linear model that incorporates the baseline measure as a covariate, the stratification factor and randomized treatment group. Pairwise comparisons of each active treatment group to control will be conducted via linear contrasts.

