## 8. STUDY DRUGS

### 8.1 Randomization

Subjects will be randomized to one of three treatment groups using a permuted block randomization algorithm supplied by a statistician blinded to patient data.

NASH without insulin resistance or diabetes may be clinically different to NASH with pre-diabetes or diabetes. Equal numbers of patients in each treatment arm is targeted. Randomization will be proportional (1:1:1) and stratified by Baseline HBA1C  $\leq 6.0$  or  $>6.0 - 9.0$ . (See [Section 7.2.2](#) and the Study Reference Manual)

Additionally, to ensure baseline Hepatic Fat Fraction (HFF) would not be a confounding factor, subjects will be stratified for baseline HFF according to the following groups  $\leq 10\%$ ,  $10\% < X \leq 20\%$ ,  $20\% < X < 30\%$  and  $\geq 30\%$ .

If a subject discontinues from the study, the randomization code will not be reused, and the subject will not be allowed to re-enter the study.

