#### Fat Liver Content Change from Baseline:

The current sample size of 40 subjects per group should yield approximately 85% power to detect a treatment effect of at least -5% with respect to the difference in the mean change from Baseline between one of the IMM-124E treatment groups and placebo assuming a standard deviation (SD) of 7.3% ( $\alpha=0.05$ ; two-tailed; unpaired t-test). The SD of 7.3% for the change from Baseline endpoint was derived assuming 1) SDs of 6% for each timepoint, 2) equal variances in each treatment group and 3) a low to moderate correlation of 0.25 between pre- and post-Baseline measurements.

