3.1 Analysis populations

The Safety population will consist of all subjects who received at least one dose of study drug. All safety analyses will be analysed based on the treatment actually received. A subset of the safety population will be the Early Termination (ET) population. The ET population will consist of all subjects who withdrew after being randomised but before completing the Week 24 visit.

The Intention-to-Treat (ITT) population will consist of all subjects who were randomised, regardless of whether they received study drug or not. This population will be tested only if at least one subject was randomised but did not receive any study drug. All efficacy analyses will be based on the treatment to which each subject was randomised.

Full Analysis Set (FAS) for efficacy includes all subjects who received at least one dose of study medication. Only subjects with clear documentation that no study medication was received may be excluded. In the event of treatment allocation errors, subjects will be analysed for efficacy according to the treatment to which they were randomised. The FAS population will consist of the same set of patients as the Safety population. The only difference between the Safety and FAS populations will be the treatment group patients are analysed in, if any misallocation of treatment occurs.

The per protocol (PP) population will consist of all subjects who were randomised, completed the entire 24 week treatment period, were at least 85% - 115% compliant with the study drug, had liver MRIs at baseline and Week 24 and had no major protocol violations. Major protocol violations are deviations decided and documented prior to data lock and un-blinding of the randomisation code presumed by the medical monitor of having significant potential to distort the results of the study such as where a patient has been given an incorrect dispense or where they failed to satisfy inclusion or exclusion criteria. The PP population will be analysed according to the group to which they were randomised.

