Sensitivity analyses will be performed in the final study analysis and will use the same analysis method on the FAS and PP populations using the multiple imputation and analysis method to impute missing values and, finally, an analysis using the full set of ITT population data, but including study centre as an additional main effect.

Interaction effects with study centre will not be investigated. If any outliers are detected (defined as greater than ± 2 SD away from the mean for that group and visit combination), sensitivity analyses will be performed where those outliers are removed and then will be compared with the analysis where those outliers were not taken out.

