12. TABLE AND FIGURE LISTINGS

Table Section	Table Title (Population)
Section 10.1	Subject disposition (usually from Clean File document)
Section 10.2	Protocol deviations (usually compiled by medical writers from listing)
Section 11.1	Analysis populations
Section 11.2	Demographics (FAS population)
	Prior Medical History events (FAS population)
	Current Medical History events (FAS population)
	Prior medications ceased before study treatment (FAS population)
	Concomitant medications taken during study (FAS population)
	New medications commenced after start of study treatment (FAS population)
	Histological results from liver biopsy prior to Screening (FAS population)
Section 11.3	Compliance (ITT, PP, FAS populations)
Section 11.4	Hepatic fat fraction (ITT population)
	Analysis of change in hepatic fat fraction (ITT population)
	Hepatic fat fraction (FAS population)
	Analysis of change in hepatic fat fraction (FAS population)
	Hepatic fat fraction (PP population)
	Analysis of change in hepatic fat fraction (PP population)
	Analysis of hepatic fat fraction using multiple imputation and analysis method (ITT population)
	Analysis of hepatic fat fraction using multiple imputation and analysis method (FAS population)
	Analysis of hepatic fat fraction with site as stratification factor (ITT population)
	Analysis of hepatic fat fraction with site as stratification factor (FAS population)
	Analysis of hepatic fat fraction with site as stratification factor (PP population)
	Hepatic fat fraction with Hepatic fat fraction sub-groups as stratification factor (ITT population)
	Hepatic fat fraction with Hepatic fat fraction sub-groups as stratification factor (FAS population)
	Hepatic fat fraction with Hepatic fat fraction sub-groups as stratification factor (PP population)
	Hepatic fat fraction with Fibrosis sub-groups as stratification factor (ITT population)
	Hepatic fat fraction with Fibrosis sub-groups as stratification factor (FAS population)
	Hepatic fat fraction with Fibrosis sub-groups as stratification factor (PP population)
	Hepatic fat fraction with Ballooning sub-groups as stratification factor (ITT population)
	Hepatic fat fraction with Ballooning sub-groups as stratification factor (FAS population)

population)

Hepatic fat fraction with Ballooning sub-groups as stratification factor (PP population)

Hepatic fat fraction with HbA1c sub-groups as stratification factor (ITT population)

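### The planned multiple imputation of liver fat is empty in the per-protocol set, unspecified in the FAS and ITT, and never departs from missing at random

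*SAP*

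**What the plan says.** SAP 7.2 analyses change in hepatic fat fraction by analysis of variance, with treatment and a subgrouping variable in the model. Missing values stay missing in the primary analysis. For the final analysis the sensitivity work "will use the same analysis method on the FAS and PP populations using the multiple imputation and analysis method to impute missing values", followed by an ITT analysis with centre added.

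SAP 3.1 admits a subject to the per-protocol (PP) set only if, among other conditions, the subject "had liver MRIs at baseline and Week 24 and had no major protocol violations". The FAS needs only one dose of study drug.

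The table list in SAP 12 includes "Analysis of hepatic fat fraction using multiple imputation and analysis method (ITT population") and the same table for the FAS. It has none for PP. Two figure titles there name ITT, PP and FAS with imputation where appropriate.

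SAP 3.3 names multiple imputation as a general technique with two references, and adds an analysis of the imputed data with and without centre. It does not give the imputation variables, the number of imputations or the missingness assumption. Neither document plans a delta-adjusted, reference-based or tipping-point analysis, although Protocol 12.4 says that the SAP will set out how missing values are handled and which sensitivity analyses are run.

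The Protocol synopsis says that sample size and power "have not been adjusted for multiple comparisons or multiple endpoints, dropouts or stratification". Protocol 11.5 replaces early withdrawals.

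**The concern.** A missing-data sensitivity analysis should ask whether the conclusion survives a different assumption about the subjects who left. As written, one of its two named populations has no missing outcome. In the other, the obvious default imputation makes the same assumption as the primary analysis: subjects who left resemble completers with the same arm and baseline category. Agreement between the two results could then be reported as robustness when it follows largely from the construction. If subjects doing poorly on active treatment leave more often, both estimates favour the drug by the same amount.

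The two SAP sections also name different populations, so a programmer cannot follow both. Because the imputation model is open, it could be chosen after unblinding.

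**Working it through.** **1. The plan's own figure.** Protocol 12.1: "The current sample size of 40 subjects per group should yield approximately 85% power to detect a treatment effect of at least -5" percentage points, with SD 6 at each time point and "a low to moderate correlation of 0.25 between pre- and post-Baseline measurements".
- SD of change = sqrt(36 + 36 - 2 x 0.25 x 36) = sqrt(54) = 7.35 (stated 7.3).
- Standard error = 7.3 x sqrt(2/40) = 1.632, and 5/1.632 = 3.063. Power = Phi(3.063 - 1.960) = 86.5% (normal) or 85.7% (t). The stated figure reproduces.
- With no replacement and assumed losses of 10, 20 or 30%, n per arm is 36, 32 or 28 and power is 82.8, 78.2 or 72.7% (normal).

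**2. PP set.** Both MRIs are an entry condition, so the number of missing outcomes is 0 by definition.

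**3. FAS and ITT.** A valid baseline MRI result is needed before randomization (Protocol 7.2.2 and 7.2.3). The only other scheduled MRI is at Week 24 or early withdrawal (Protocol Table 1 and 7.2.9). So what can be missing is the follow-up value.

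**4. Why default imputation repeats the complete-case answer.** Let b be the complete-case least-squares coefficients, X_o and X_m the design rows with observed and missing outcome, and X all rows. Imputed values drawn from the same model average X_m b. Refitting gives

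(X'X)^-1 (X_o'y_o + X_m'X_m b) = (X'X)^-1 (X_o'X_o b + X_m'X_m b) = b.

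The two estimates differ only by imputation noise, whatever caused the dropout.

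**5. Simulation.** 600 trials per row and dropout rate; 40 per arm; true effect -5; SD 6; correlation 0.25; 30 imputations. The analysis is ANOVA on change with treatment and the SAP's fat categories. Assumptions not in the documents: mean baseline 18%, dropout 10/20/30% per arm (random in placebo), and an interim marker with residual correlation 0.5. Cells show mean complete-case / mean imputed estimate.

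| Active-arm dropout depends on | Imputation model | 10% | 20% | 30% | Significance differs (0.04695) |
|---|---|---|---|---|---|
| unseen outcome | analysis variables | -5.62 / -5.62 | -6.21 / -6.21 | -6.74 / -6.74 | 0.0 / 0.5 / 0.7% |
| unseen outcome | continuous baseline + marker | -5.72 / -5.49 | -6.20 / -5.82 | -6.87 / -6.35 | 1.2 / 2.0 / 1.8% |
| the marker | continuous baseline + marker | -5.40 / -5.06 | -5.67 / -5.00 | -6.04 / -5.11 | 3.0 / 6.8 / 8.8% |
| baseline fat | continuous baseline | -4.90 / -4.98 | -4.86 / -5.02 | -4.76 / -5.00 | 1.8 / 4.8 / 7.3% |

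With the analysis variables alone, the mean estimates agreed within 0.01 under every mechanism tried. The mean absolute gap in a single trial was 0.07, 0.10 to 0.11, and 0.12 to 0.14 points at the three dropout rates. A richer model removes most of the bias when the marker drives dropout. It removes only part when the unseen outcome does: at 30%, 6.87 - 6.35 = 0.52 of an excess of 1.87.

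**6. Size of a false effect.** Assume no true effect, 4 of 40 placebo subjects lost at random and 8 of 40 active subjects lost.
- Random active loss: bias 0.
- Exactly the worst 8 lost: the retained best 80% of a normal distribution has mean shift phi(0.842)/0.80 = 0.280/0.80 = 0.35 SD. The residual SD given baseline is 6 x sqrt(1 - 0.0625) = 5.81. Bias = 0.35 x 5.81 = 2.03, so about -2 points. Simulating this case with the SAP's fat categories in the model gives -1.97.
- Intermediate strengths of selection gave -0.7 to -1.6 for both complete-case and imputed estimates (correlation 0.99). That run adjusted for continuous baseline, which is not the SAP's model.

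**The case against.** A reader might infer that the sensitivity analysis cannot disagree with the primary result. The documents do not support that. SAP 3.3 leaves the imputation model open and nothing excludes interim ALT, weight or HbA1c. The SAP's ANOVA uses fat categories, so even a continuous baseline in the imputation adds information. The last two rows of the table show real differences. This objection stands, and it is why the criticism is of an unspecified model.

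A reader might also infer that subjects who leave never have a follow-up MRI, or that informative dropout would go wholly unseen. Neither follows. Protocol 7.2.9 schedules MRI at early withdrawal, and Protocol 11.3 encourages subjects who stop drug to stay for outcome measurement. SAP 8.6 describes the early terminations: reasons, timing, baseline values, and last ALT and HbA1c. But the SAP does not say whether a withdrawal MRI counts as Week 24, and the SAP 8.6 summary does not adjust the treatment estimate.

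The PP slip is partly mended by the SAP 12 table list. Biopsy subgroup factors may still be missing in PP, because SAP 7.2 uses biopsies up to 6 months before screening and eligibility allows 12. That is a missing covariate; the outcome is still complete.

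Finally, the trial calls itself exploratory and no dropout rate is given. Both points limit how much weight any single bias figure can bear.

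**Conclusion.** The point holds in a limited form. Imputing the outcome in PP does nothing, and SAP 7.2 and 12 disagree on the populations. In FAS and ITT, imputation from the analysis variables alone is close to a restatement of the complete-case result, including any bias from outcome-dependent dropout. It becomes informative only with added predictors, and even then it stays within missing at random. The analyses with centre and with outliers removed do not test that assumption.

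The possible false effect lies between 0 and about -2 points, at most some 40% of the planned 5. That range rests on the assumed losses of 4 and 8 per 40 and on the Protocol's SD and correlation. It is not a forecast. This is a worthwhile, cheap improvement to an exploratory trial and does not invalidate the primary analysis.

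**What to change.** - In SAP 7.2 replace FAS and PP by ITT and FAS, to match the table list in SAP 12, and take PP out of the imputed figure titles.
- Specify the imputation model by arm: continuous baseline hepatic fat fraction; post-baseline ALT, AST, weight and HbA1c, all already collected; and reason for withdrawal. State the number of imputations. With 28 to 36 observed values per arm at 10 to 30% loss, keep the list short. Reason for withdrawal can inform the model only where some subjects with that reason have a follow-up MRI.
- State whether an early-withdrawal MRI counts as the Week 24 value or enters only as a predictor.
- Add a delta-adjusted tipping-point table: worsen imputed Week 24 liver fat in the active arms in 1-point steps and report the shift at which the conclusion changes.
- Fix all of this before unblinding.

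The cost is a little SAP text and programming, one extra table, and possibly a less favourable statement on robustness.
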